3.2 Methods of Assigning Subjects to Treatment Groups

Approximately 130 subjects (65 per arm) will be randomized to treatment with lirentelimab SC or placebo SC in a 1:1 ratio. Stratified permuted block randomization will be used. Randomization will be stratified based on UAS7 score (16–27 vs. 28–42) and on Omalizumab experience for the treatment of CSU (omalizumab-exposed vs. omalizumab-naïve). An Interactive Response Technology System (IRT) will be used to perform the randomization.

3.3 Treatment Blinding

This is a double-blind study. The identity of active and placebo treatments will not be known to Investigators, Sponsor (including safety monitor), research staff (including pharmacy), subjects, or the study monitor.

3.4 Determination of Sample Size

A sample size of 55 subjects per treatment group will provide >90% power to demonstrate a statistically significant difference between lirentelimab and placebo in achieving a reduction in UAS7. We hypothesized a mean difference of at least 8 between lirentelimab SC and placebo SC, and a pooled standard deviation of 11. This calculation is based on results derived from the AK002-006 study and expected placebo response rates reported in previously published data in H1-AH refractory CSU.

Randomization of up to 130 subjects (approximately 65 subjects per treatment group) is driven by the powering calculations, the likely dropout rate of up to approximately 10%, and will further support the evaluation of the safety and tolerability of lirentelimab SC.

4. Definitions

4.1 Terminology and Definitions

Terminology	Definition
Baseline	Baseline for non-daily assessment (e.g., laboratory tests) is defined as the non-missing value collected most recently to and before the time of the very first dose of study drug. Baseline Patient Reported Outcome (PRO) data will be the average or the sum of the weekly PRO data collected in the last 7 days prior to Day 1 depending on the outcome under consideration.
Concomitant Medications and Procedures	Medications and procedures with a stop date before the treatment dosing date will be considered prior medications/procedures. Medications and procedures with a start or stop date on or after the treatment dosing date will be considered concomitant. All medications/procedures marked as ongoing are concomitant.
Study Day	Study Day 1 is defined as the date on which a subject received the first dose of study drug. For visits prior to the first dose of study drug, Study Day is calculated as Visit Date – Day 1 Date. For visits after the first dose, Study Day is calculated as Visit Date – Day 1 Date +1.
Study Week	Study Week for PRO analysis is defined as 7 days a week starting from the day of first dose (Day 1). Details are provided in Section 5.2.

Table 7Terminology and Definitions

4.2 Target of Estimation

The estimand for the AK002-027 study estimates the effect of treatment, while considering treatment adherence and response. The estimand will provide an answer to the question that is crucial to individual subjects: "If I take this study medication as part of my treatment regimen, without adding any further drugs that may impact the underlying disease or exit the study prematurely, what improvement in CSU might be anticipated after 12 weeks?"

The sections below describe the attributes of the estimand consistent with the ICH E9 (R1) Addendum (FDA, 2021).

4.2.1 **Population Targeted by the Scientific Question**

The population targeted by the scientific question is defined via the inclusion and exclusion criteria as part of the study protocol. Subjects may be male or female and must have a clinical diagnosis of CSU as defined by the study inclusion criteria.

Allakos Inc.

Confidential

4.2.2 Variables of Interest (or Endpoint) to be Obtained for Each Subject that is Required to Address the Scientific Question

The primary endpoint to be obtained for each subject in this study to address the scientific question is change from baseline in UAS7 score at Week 12.

4.2.3 Treatment

Lirentelimab SC or placebo SC administered to subjects on Days 1, 15, 29, 43, 57, and 71 for a total of 6 doses.

4.2.4 Intercurrent Events

The events below are considered intercurrent events (ICE) potentially confounding with the efficacy outcomes.

- Premature discontinuation from the double-blind portion of the study
- Use of prohibited medications during the study
- Use of rescue medication for symptoms of CSU during the study

4.2.5 Strategy for Handling Intercurrent Events

For subjects who experienced an ICE of premature discontinuation from the double-blind portion of the study, efficacy outcome will be defined as "non-responder", referred to as non-response imputation, for binary endpoints and will be set to missing for continuous endpoints from the point when that ICE occurs. An appropriate method for handling missing data through statistical modeling (e.g., multiple imputation [MI]) will be used.

During the double-blind portion of the study, use of the following prohibited medications for reasons unrelated to CSU or rescue medications for the purposes of alleviating symptoms of CSU (see Appendix 1) will be deemed an ICE and efficacy data for the affected subject will be handled as follows:

- Antihistamines Use of any new H1-AH or additional doses of an H1-AH above the stable baseline dose are prohibited. Subject-entered data for the day after the prohibited medication was used will be set to missing and this will apply for each day of prohibited medication use.
- Systemic corticosteroids Use of systemic corticosteroids at any dose and for a duration of less than 3 consecutive days will result in the subject's efficacy data for a period of 7 calendar days will be set to missing beginning with the first day of systemic corticosteroid use and extending to a 7 day period following the last dose. Use of systemic corticosteroids for 3 or more days will result in censoring of all efficacy data from the first day of corticosteroid treatment, i.e., this

censoring rule is equivalent to using all the data up to first day of corticosteroid treatment. An appropriate method for handling missing data through statistical modeling (e.g., multiple imputation [MI]) will be used for continuous endpoints. For binary endpoints, efficacy outcome will be set to non-responder status.

• Immunosuppressants, Immunomodulators and Biologics – Use of any immunomodulator, immunosuppressant or biologic will result in the premature withdrawal of the subject from the study and the censoring of all efficacy from the initiation of that therapy, i.e., this censoring rule is equivalent to using all the data up to first day of the prohibited therapy. An appropriate method for handling missing data through statistical modeling (e.g., multiple imputation [MI]) will be used for continuous endpoints. For binary endpoints, efficacy outcome will be set to non-responder status.

Blinded adjudication of prohibited medication uses for rescue or for reasons unrelated to symptoms of CSU will be implemented before database lock.

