2.1.1 Weekly Urticaria Assessment Score (UAS7)

The UAS7 is the sum for 7 days of the daily Hives Severity Score (HSS) and the daily Itch Severity Score (ISS). The possible range of the weekly UAS7 score is 0–42. Complete UAS7 response is defined as UAS7 = 0 or by reduction of \geq 90% from baseline.

The severity of hives will be recorded by all subjects once daily in their Urticaria Patient Daily Diary (UPDD), on a scale of 0 (none) to 3 (> 50 hives) (see Table 1). A weekly HSS score (HSS7) is derived by adding the average daily scores of the 7 days preceding the visit. Therefore, the possible range of the weekly score is 0 - 21. A complete hives response is defined as HSS7 = 0. When one or more of the daily scores are missing, the following principles will be applied to handle the missing data:

- At baseline and post-baseline time points, if a subject has at least 4 non-missing daily scores within a given week, the weekly score is calculated as the sum of the available scores in that week, divided by the number of days that have a non-missing diary score, multiplied by 7.
- At post-baseline time points, if there are less than 4 non-missing daily scores within a given week, then the weekly score is set to missing. Missing data will be imputed using methods outlined in Section 6.9.1. It is worth remarking that missing data imputation is not required at baseline since a minimum of 4 daily scores per week are required to determine subject eligibility for the study.

Score	Number of Hives per 24 Hours
0	None
1	< 20
2	20-50
3	> 50

Table 1Hives Severity Score

The severity of itching will be recorded by all subjects once daily in their UPDD, on a scale of 0 (none) to 3 (severe) (see Table 2). A weekly ISS score (ISS7) is derived by adding the average daily scores of the 7 days preceding the visit. Therefore, the possible range of the weekly score is 0 - 21. Partially missing diary entries will be handled in the same way described for the hives severity score.

A complete itch response is defined as ISS7 = 0.

Score	Pruritus (Itch) over the last 24 Hours		
0	None		
1 Mild (present but not annoying or troublesome)			
2	Moderate (troublesome but does not interfere with normal daily activity or sleep)		
3	Severe (severe itching, which is sufficiently troublesome to interfere with normal daily activity or sleep)		

Table 2Itch Severity Score

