6.9.2 Analysis of Secondary and Exploratory Efficacy Endpoints

The binary secondary and exploratory efficacy endpoints will be analyzed using the Cochran-Mantel-Haenszel test adjusted by omalizumab experience for the treatment of CSU (exposed, naïve), UAS7 score (16–27, 28–42), and region (U.S., non-U.S.) at Week 12. A sample SAS code is as follows:

```
* COMPUTES CMH P-VALUE AND NEWCOMBE COMMON RISK DIFFERENCE ;
ods output CMH=PVAL(where=(althypothesis='Row Mean Scores Differ'))
CommonPdiff=DIFF;
proc freq data=ADEF ;
      tables UAS7*OMALIZUMAB_EXPERIENCE*REGION*TRTP*RESP / cmh(MF)
commonriskdiff
(cl=NEWCOMBE) ;
run ;
```

The Mantel-Fleiss (MF) criterion will be performed, and if it is not met while using the option CMH (MF) in SAS procedure PROC FREQ, analyses including each factor separately in CMH test will be conducted. Should assumption per the MF criterion not be satisfied, the comparison will be based on a Fisher's exact test after collapsing across levels of the stratification factor and country.

Below is an example of the SAS code for the Fisher's exact test:

```
* COMPUTE 95% EXACT CONFIDENCE INTERVAL FOR %RESPONSE FOR INDIVIDUAL
TREATMENT ;
ods output BinomialCLs=CL ;
proc freq data=ADEF ;
    table RESP / out=CNTS bin(cl=midp) ;
    by TRTP ;
run;
* COMPUTE 95% EXACT CONFIDENCE INTERVAL AND FISHERS EXACT P-VALUE FOR
BETWEEN TREATMENT DIFFERENCE ;
ods output FishersExact=PVAL(where=(name1='XP2_FISH'))
RiskDiffCol2=DIFF(where=(row='Difference') ;
proc freq data=ADEF ;
    table TRTP*RESP / riskdiff(cl=exact) exact ;
run ;
```

For the analysis described above, missing data from subjects who prematurely discontinue the randomized treatment, initiate any treatment adjustments as outlined in Section 4.2.5 (e.g., use of prohibited or rescue medication), or missing daily PRO scores as described in Section 2.1 will be imputed using non-response imputation.

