To assess the impact of the above "non-responder" rule, the missing data strategy will employ mixed model for repeated measures (MMRM) technique. This approach assumes missing observations are missing at random and borrows information from subjects in the same treatment group considering the missingness of data through the correlation of the repeated measurements. The SAS procedure PROC GLIMMIX will be used for this purpose. The model will include treatment, region, omalizumab experience for the treatment of CSU (exposed, naïve), UAS7 score (16–27, 28–42), visit, and treatment-by-visit-interaction as fixed categorical effects, and baseline and baseline-by-visit-interaction as fixed categorical effects, standard error, two-sided 95% confidence interval for odds ratio and p-values at time points of interest.

All secondary and exploratory efficacy endpoints of continuous nature will utilize MMRM procedure after applying the primary censoring rule, i.e., the rule will censor data after permanent study drug discontinuation or after rescue therapy that applies the censoring rule as described in Section 4.2.5. This censoring rule is equivalent to using all the data up to discontinuation or rescue.

The MMRM model will include fixed effects for baseline value, omalizumab experience for the treatment of CSU (exposed, naïve), UAS7 score (16–27, 28–42), country, treatment, study week, the treatment-by-week interaction, and the baseline-by-week interaction and allow for random subject effects. Treatment and week will each be fitted as categorical variables. The model will assume unstructured covariance structure. If the model with unstructured covariance does not converge, then other covariance structures will be considered to model the within-subject errors. The Kenward-Allakos Inc. Page 36 of 49 *Confidential*

Rogers approach for computing denominator degrees of freedom will be used to account appropriately for pooling of within-subject and between-subject variance estimates. The LS and 95% CI for the difference between groups will be estimated using the simple contrast at each time point. Below is an example of the SAS code for the MMRM:

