9.2 Appendix 2: List of Tables, Figures, and Listings

9.1 Appendix 1: Intercurrent Events and Listing of Prohibited Medication/Treatments and Potential Rescue Medications for CSU

Prohibited medications are defined as therapies that should not be taken during the course of the study either because of a potential impact on the assessment of efficacy and/or subject safety. Rescue medications/treatments are defined as any therapy or treatment taken during the course of the study for the specific purpose of alleviating CSU symptoms that may have an impact on the assessment of efficacy and includes: systemic medications such as systemic corticosteroids, increased daily dose or addition of a new H1-AHs, immunosuppressants, immunomodulatory medications, and biologics. Detailed definitions of ICE and data handling strategy for ICE are described in section 4.2.5.

The following provides the details of the prohibited medications/therapies for this study:

- The use or initiation of any new H1-AH or increase in the total daily dose, as compared to baseline, of an H1-AH for the purpose of treating CSU at any point in the study will be considered rescue therapy H1-AH: ATC code is R06A
- 2) The use or initiation of topical corticosteroids for the purpose of treating skin conditions other than CSU at any point in the study will be not be considered rescue therapy but should be avoided if possible. If unavoidable, lower potency topical steroids over the least surface area possible and for the shortest duration should be utilized: ATC code is D07A High Potency TCS: ATC codes D07AC or D07AD Low or moderate potency TCS: ATC code D07, excluding D07AC or D07AD
- Prohibited systemic medications (including systemic corticosteroids, H2-AH, immunosuppressants, immunomodulators, hydroxychloroquine, oral doxepin, IV immunoglobulins, and biologics)

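### SAP 4.2.5 gives no non-responder rule for antihistamine intercurrent events, so a rescued subject can count as UAS7 = 0, contrary to Protocol 9.3 and 16.6.2

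*SAP*

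**What the plan says.** SAP 4.2.5 introduces its medication bullets by saying that the listed uses, whether for CSU or for other reasons, "will be deemed an ICE and efficacy data for the affected subject will be handled as follows". For antihistamines the whole data rule is "Subject-entered data for the day after the prohibited medication was used will be set to missing and this will apply for each day" of use. The corticosteroid and the immunosuppressant/biologic bullets each close with "For binary endpoints, efficacy outcome will be set to non-responder status", and the paragraph on premature discontinuation gives the same outcome. The antihistamine bullet has no such sentence. SAP Appendix 1 nevertheless lists "increased daily dose or addition of a new H1-AHs" among rescue treatments.

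SAP 2.1.1 calculates a weekly score "if a subject has at least 4 non-missing daily scores within a given week". SAP 6.9.2 covers missing data from subjects who discontinue or "initiate any treatment adjustments as outlined in Section 4.2.5 (e.g., use of prohibited or rescue medication"), and says that these, or "missing daily PRO scores as described in Section 2.1 will be imputed using non-response imputation".

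The protocol is more direct. Section 9.3 calls new or increased H1-AH for CSU rescue, and treats rescued subjects as non-responders in the evaluation of data. Section 9.2 calls an H1-AH dose increase, for CSU or another reason, rescue with non-responder status. Section 16.6.2 and the synopsis assign non-response on binary endpoints to subjects with an ICE before the end of Week 12. SAP 1 states that the SAP replaces the protocol's statistical methods.

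**The concern.** H1-AH escalation is the one ICE in SAP 4.2.5 with no binary outcome attached. Read literally, two kinds of rescued subject keep an observed Week 12 score that can be 0: those whose extra H1-AH ended before it could delete a Week 12 entry, and those who lose no more than 3 of the 7 entries. Neither has a missing Week 12 score for SAP 6.9.2 to impute.

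That conflicts with the protocol's non-responder rule. It also conflicts with the question that SAP 4.2 keeps for the estimand, which asks about improvement when no further drug affecting the disease is added.

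UAS7 = 0 at Week 12 is third in the fixed sequence of SAP 2.2 and 5.9. It is tested at two-sided 0.05 for a superiority statement if UAS7, HSS7 and ISS7 succeed. Two programmers following the two texts could produce different responder counts for a formal test.

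**Working it through.** The plan gives no figure for UAS7 = 0. Its only power figure is for the primary endpoint, and nothing here depends on it. The check applies the written rules to diary patterns.

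**Inputs**
- Deletion: the entry on the day after each day of use (SAP 4.2.5).
- Observed weekly score: at least 4 of 7 entries, prorated to 7 days (SAP 2.1.1).
- Week 12 window: the 7 days before the earlier of 14 days after Dose 6 or the first open-label dose. With fewer than 4 completed diaries, its start may move back as far as the day of Dose 6 (SAP 5.2).
- 65 subjects per arm (SAP 3.2).

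**Window.** With Dose 6 on Day 71 and no open-label dose before Day 85, 71 + 14 = 85, so the window is Days 78–84. The diary is otherwise complete.

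**Daily use from Day 1**

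| Extra H1-AH on | Entries deleted | Week 12 entries left | Week 12 score |
|---|---|---|---|
| Days 1–76 | Days 2–77 | 7 (Days 78–84) | observed |
| Days 1–79 | Days 2–80 | 4 (Days 81–84) | observed |
| Days 1–80 | Days 2–81 | 3 (Days 82–84) | missing, so non-response |

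The backward extension changes none of these rows. In the last row Days 71–77 are deleted too, so moving the start back recovers nothing. If Dose 6 falls on Day 66 or Day 76, the limits of the visit window, the cut-offs 76 and 79 become 71 and 74, or 81 and 84.

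**Most rescue days with a score still observed**
- Without extension: Days 1–76 plus 3 of Days 77–83, 76 + 3 = 79.
- With extension: 4 entries must survive among Days 71–84, so 14 − 4 = 10 may be deleted, by use on 10 of Days 70–83. Adding Days 1–69 gives 69 + 10 = 79.

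Either way, 79 of the 83 days from Day 1 to Day 83 can be rescue days.

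**Use confined to Days 77–83** (each day deletes one window entry)
- Possible patterns: 2^7 − 1 = 127.
- Without extension, 1 to 3 days of use keep a score: 7 + 21 + 35 = 63.
- If entries deleted for an ICE can trigger the extension, Days 74–77 supply four entries even when all seven are lost, so all 127 keep a score.

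These are counts of patterns, not probabilities. An observed score is a response only if every retained hives and itch entry is 0.

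**Deletion can create a response.** Suppose use on Days 79–81 deletes Days 80–82, each scored 6 out of 6, and the other four days are 0. The prorated UAS7 is 0 / 4 × 7 = 0. The undeleted sum is 3 × 6 = 18, above the entry threshold of 16.

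**Effect on the endpoint.** One reclassified subject moves an arm's rate by 1/65 = 1.54 points. Assuming 0 to 5 reclassified subjects in each arm, the between-arm difference changes by anything from −5/65 to +5/65, that is −7.7 to +7.7 points.

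**The case against.** The strongest reply is SAP 6.9.2. It names rescue use as a ground for non-response imputation alongside missing diary scores, which would be redundant for H1-AH if only missing scores counted. The next paragraph opens "To assess the impact of the above 'non-responder' rule". Non-response was therefore probably intended. That stands as evidence of intent. But the sentence imputes missing data, and a subject whose use stopped by Day 76 has a complete Week 12 score.

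A second reply is that silence in the SAP need not displace Protocol 9.3, which is a medication section. That is arguable, but the binary rule in Protocol 16.6.2 is a statistical method that the SAP says it replaces. Protocol 9.2 speaks of non-response at the time of a dose increase, which could be read as temporary. Protocol 16.6.2 has no such limit.

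Third, the fix reaches H1-AH taken for reasons other than CSU, which Protocol 9.3 does not call rescue. That is so for a new H1-AH. However, SAP 4.2.5 itself deems such use an ICE, Protocol 16.6.2 attaches non-response to an ICE, and Protocol 9.2 includes dose increases for other reasons. Blinded adjudication sorts uses as rescue or not, and supplies no binary rule.

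Parts of the magnitude are soft, and this stands. The 79-day figure is a boundary case. The 127 depends on a debatable reading of SAP 5.2, since a completed diary later deleted is not obviously non-compliance. An earlier open-label dose also moves the cut-offs: with Dose 6 on Day 71 and open-label dosing on Day 82, the window is Days 75–81 and they become Days 73 and 76.

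**Conclusion.** The concern holds. The H1-AH bullet lacks the binary rule that SAP 4.2.5 gives for its other ICEs. The SAP's written rules can then yield a UAS7 = 0 responder whom Protocol 9.3 and 16.6.2 count as a non-responder. Confidence is high in the omission and its logical consequence.

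The size and direction of the effect are unknown, because the documents give no rescue rates. The ±7.7 points rests wholly on the assumed 0 to 5 subjects per arm. Sustained daily use through Day 80 or later already ends as non-response when Dose 6 is on Day 71, so the gap concerns earlier or intermittent use. The primary ANCOVA is not shown to be materially affected. The text should be settled before unblinding, because it defines the responder count for a gated test.

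**What to change.** Before unblinding:

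1. Add to the antihistamine bullet of SAP 4.2.5: *For binary endpoints, any H1-AH use deemed an ICE under this section before the end of Week 12 gives non-responder status.* This matches Protocol 16.6.2.
2. Reword SAP 6.9.2 so that non-response applies to every subject with an ICE before the end of Week 12, as well as to missing Week 12 scores.
3. If the one-day deletion is wanted for UAS7 = 0, prespecify it as a sensitivity analysis.

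The cost is one sentence and one wording change. No new data are needed and no missing data are added. UAS7 = 0 rates, and power for that endpoint, may be lower than under the literal SAP text, by an amount that depends on rescue use. The change concerns data handling only, not who may receive rescue.

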4.2.6 Summary Measure of the Estimand

Least squares mean (LSM) (and standard error [SE]) of change from baseline in UAS7 to Week 12 and the between treatment difference in the lirentelimab SC and placebo SC groups LSM.

5. Statistical Methods

